Appendix 1 Schedule of Activities

	Scree	ning ^a								7	reatm	ent							Week >49		Study
Week	_	-	1	2	3	4	5	9	13	17	21	25	29	33	37	41	45	49	to Study Completion	Safety FU ^b	Completion/ Discon. c
Day ^d	–28 to –1	–7 to –1	1	8	15	22	29	57	85	113	141	169	197	225	253	281	309	337			
Informed consent	Хe																				
Demographic data	Х																				
Medical history and baseline conditions ^f	х																				
PROs, HRQoL (CATCH) ^g			Х						Х			Х			Х			Х	Q12W		х
Patient-reported outcomes (EmiPref) ^g										х											
Health status (EQ-5D-5L) ^g			Х						Х			Х			Х			Х	Q12W		х
Joint health (HJHS) h		х										Х						Х	Q24W		х
Activity i			٧	Veek	s 1–	2, W	eeks	12-	-13, V	Veek	s 24–2	25, W	eeks 3	36–37	, and	Week	s 48–	49			
Vital signs ^j	х		Х	Х	х	Х	Х	Х	Х	Х	Х	Х	х	Х	Х	Х	Х	Х	Q12W		х
Weight	х		Х				х	х	х	х	Х	х	х	Х	Х	Х	Х	Х	Q12W		х
Height k, l			Х						х			Х			х			х	Q12W		
Complete physical examination ^m	х								х			х			х			х	Q12W		х
ECG ^{, n}	х						х					Х						Х	Q12W		х
Hematology°		х	Х	х	х	Х	х	х	х	Х	х	Х	Х	х	х	Х	х	Х	Q12W		х

Appendix 1: Schedule of Activities (cont.)

	Screen	ning ^a			I		I	I	I	T	reatm	ent		ı		ı	1		Week >49	0.11	Study
Week	_	_	1	2	3	4	5	9	13	17	21	25	29	33	37	41	45	49	to Study Completion	Safety FU ^b	Completion/ Discon. c
Day ^d	–28 to –1	–7 to −1	1	8	15	22	29	57	85	113	141	169	197	225	253	281	309	337			
Chemistry ^p		Х	х	х	х	х	х	х	х	Х	х	Х	Х	х	Х	Х	Х	х	Q12W		х
Local coagulation tests (aPTT, PT/INR)			х	х	х	х	х	х	х	х	х	х	х	х	х	х	х	х	Q12W	х	х
Pregnancy test ^q		Х	х				х	х	х	Х	Х	Х	Х	Х	Х	Х	Х	х	Q12W	Х	х
Emicizumab administration ^r			х	х	х	х		To	o be	admir	nistere	ed QV	/, Q2\	N, or	Q4W	deper	nding	on reg	gimen		
Samples for PK, PD, ADA, and biomarkers											Se	ee Ap	pend	ix 2.							
BMQ s												QW a	nd or	n day	s of b	leed					
BMQ review ^t			х	х	х	х	х	х	х	Х	х	Х	Х	Х	Х	Х	х	х	Q4W	х	х
MBQ ^u			х				х	х	х	Х	х	Х	Х	Х	Х	Х	х	Х	Q4W	х	х
MD with PBAC ^u											Montl	nly							Monthly	Х	х
Concomitant medications	X^v	\mathbf{X}^v	\mathbf{X}^v	х	х	х	х	х	х	Х	х	Х	Х	х	Х	Х	Х	Х	Q4W	х	х
Adverse events w	х	x x Ongoing																			

ADA=anti-drug antibody; BMQ=Bleed Medication Questionnaire; CATCH=Comprehensive Assessment Tool of Challenges in Hemophilia; Discon.=discontinuation; eCRF=electronic Case Report Form; EmiPref=Emicizumab Preference Survey; EQ-5D-5L=European Quality of Life 5-Dimension, 5-Level Questionnaire; FU=follow-up; FVIII=factor VIII; HJHS=Hemophilia Joint Health Score; HRQoL=health-related quality of life; NA=not applicable; PD=pharmacodynamic; PK=pharmacokinetic; PRO=patient-reported outcome; QW=once a week; Q2W=every 2 weeks; Q4W=every 4 weeks; Q12W=every 12 weeks; UV=unplanned visit; MBQ=Menstrual Bleeding Questionnaire; MD=Menstruation Diary; PBAC=Pictorial Blood Assessment Chart

Notes: All study visits and assessments should be performed within ± 2 days of the scheduled visit, until safety follow-up visit. Safety follow-up visit should be performed 24 weeks after discontinuation of emicizumab; deviation of ± 7 days is acceptable. Safety follow-up visit will not be

Emicizumab—F. Hoffmann-La Roche Ltd

Appendix 1: Schedule of Activities (cont.)

performed for patients who transfer to commercial emicizumab. On treatment days, all assessments should be performed prior to emicizumab dosing, unless otherwise specified. On treatment days, all PRO assessments, when applicable, should be performed prior to any study intervention.

- ^a Results of standard-of-care tests or examinations performed prior to obtaining informed consent and within 28 days prior to Day 1 may be used; such tests do not need to be repeated for screening.
- b Patients who discontinue study drug will return to the clinic for a safety follow-up visit 24 weeks after their final dose of study drug.
- c Study completion/discontinuation visit occurs when the patient completes 52 weeks of emicizumab treatment in the study and either transfer to commercially available emicizumab or receive further emicizumab per Roche Global Policy on Continued Access to Investigational Medicinal Products; OR patient has completed the 24-week safety follow-up visit after emicizumab discontinuation; OR patient has withdrawn consent; OR patient is lost to follow-up.
- d Assessments can deviate from planned schedule by ±2 days until safety follow-up visit. Safety follow-up visit should be performed 24 weeks after discontinuation of emicizumab; deviation of +7 days is acceptable. Safety follow-up visit will not be performed for patients who transfer to commercial emicizumab.
- ^e Informed consent must be documented before any study-specific screening procedure is performed and may be obtained more than 28 days before initiation of study treatment.
- f Collected from patient's medical record and documented in the eCRF.
- ⁹ Questionnaire will be self-administered before the patient receives any information on disease status, prior to the performance of non-PRO assessments, and prior to the administration of study treatment. For patients younger than 18 years of age, the patient's caregiver will also be asked to fill out the EmiPref (caregiver version). For patients <12 years old: only the caregiver will fill out the EmiPref (caregiver version); the EmiPref (patient version) and EQ-5D-5L will not be completed.
- ^h HJHS will be performed as part of the physical examination for patients ≥ 4 years of age.
- ⁱ Applicable to patients ≥5 years of age. Accelerometer should be worn on the wrist continuously for 24 hr/day for 14 days at each 2-week period indicated.
- ^j Includes respiratory rate, pulse rate, and systolic and diastolic blood pressure while the patient is in a seated position, and temperature.
- ^k Height assessment at Day 1 only for adults.
- Height assessments for adolescents at Day 1 and ideally at all drug administration and PK sampling visits at the investigational site, but at least Q12W (repeated assessments).
- ^m Includes evaluation of the head, eyes, ears, nose, and throat, and the cardiovascular, dermatologic, musculoskeletal, respiratory, gastrointestinal, genitourinary, and neurologic systems.

Emicizumab—F. Hoffmann-La Roche Ltd

Appendix 1: Schedule of Activities (cont.)

- ⁿ If screening ECG is abnormal, repeat at Week 1. ECGs will also be performed: once during Weeks 4–8 and once 24 and 49 weeks after starting emicizumab.
- Pre-dose: WBC count, RBC count, hemoglobin, hematocrit, platelet count, and absolute differential count (neutrophils, eosinophils, basophils, monocytes, lymphocytes, other cells), mean corpuscular volume, mean corpuscular hemoglobin, mean corpuscular hemoglobin concentration, and RBC distribution width will be performed locally. Laboratory assessments completed at the screening visit do not have to be repeated at Week 1 if the period between screening and Week 1 is 5 days or less and there has been no change in health status as assessed by the investigator.
- Pre-dose: sodium, potassium, glucose, BUN, creatinine, calcium, phosphate, magnesium, total and direct bilirubin, albumin, ALP, ALT, AST, LDH and CPK will be performed locally. Laboratory assessments completed at the screening visit do not have to be repeated at Week 1 if the period between screening and Week 1 is 5 days or less and there has been no change in health status as assessed by the investigator.
- ^q All women of childbearing potential (including those who have had a tubal ligation) will be required to have a negative serum pregnancy test result at screening and within 7 days prior to initiation of study medication (Day –7 to Day –1). If applicable, urine pregnancy tests will be performed at the scheduled visits, except for Weeks 2–4. If a urine pregnancy test is positive, it must be confirmed by a serum pregnancy test. If the serum pregnancy test is positive, further administration of emicizumab should be discontinued.
- ^r Emicizumab may be administered by a mobile nursing professional.
- Bleed information for each bleed (start date and time, reason, type, location, and associated symptoms (only collected for muscle and joint bleeds in patients 12 years of age and older)) and medication for bleeds (breakthrough bleeds) should be reported by the patient via an electronic, handheld device when a bleed occurs or at least on a weekly basis (retrospective reporting for last 7 days). If the patient discontinues study treatment, bleed and bleed medication data should be provided by the patient until the safety follow-up visit (24 weeks after final study drug administration). Emicizumab doses should be recorded by the patient in the BMQ starting on Day 1.
- t Investigator review of bleed information.
- ¹¹ All female patients of childbearing potential will be asked to provide the start and end dates of menstruation that will be recorded on eCRF and to complete the MBQ and the MD with PBAC, both on paper. The MBQ will be self-administered in the clinic on Day 1 and subsequently every 4 weeks; the MD with PBAC will be completed by patients at home. The MD with PBAC will be given to patients on Day 1 and should be completed monthly on days of menstruation. The patient should return the completed MD with PBAC to the site personnel during the next clinic visit. The MD with PBAC is a monthly form that will be given in multiple copies to the patients to cover the length of the study.
- ^v Medication (e.g., prescription drugs, over-the-counter drugs, vaccines, herbal or homeopathic remedies, nutritional supplements) used by a patient in addition to protocol-mandated treatment from 4 weeks prior to enrollment to the study completion/discontinuation visit. FVIII taken during the week prior to starting emicizumab (i.e., week prior to Day 1) will also be collected on the *Hemophilia History Medication 7 Days*Prior to Enrollment eCRF page for patients who will continue their prior FVIII prophylaxis during the first week of the study.

Emicizumab—F. Hoffmann-La Roche Ltd 96/Protocol BO41423, Version 3

Appendix 1: Schedule of Activities (cont.) We After informed consent has been obtained but prior to initiation of study drug, only serious adverse events caused by a protocol-mandated intervention should be reported. Adverse events will be collected on an ongoing basis throughout the study. Injection-site reactions will be collected on a separate form from the adverse event form. After initiation of study drug, all adverse events will be reported until 24 weeks after the final dose of emicizumab. After this period, the Sponsor should be notified if the investigator becomes aware of any serious adverse event

Emicizumab—F. Hoffmann-La Roche Ltd 97/Protocol BO41423, Version 3

that is believed to be related to prior study drug treatment (see Section 5.6).

Appendix 2
Schedule of Pharmacokinetic, Immunogenicity, and Biomarker Samples

Assessments	Screening							Tre	eatme	ent P	erioc	i						Week >49	Safety	Study
Week		1	2	3	4	5	9	13	17	21	25	29	33	37	41	45	49	to Study Completion	FU Visit	Completion/ Discon. a
Day	−28 to −1	1	8	15	22	29	57	85	113	141	169	197	225	253	281	309	337			
Blood sample for genotyping b, c, f		х																		
Emicizumab PK (plasma) b		х	х	х	х	х	х	х	х	х	х	х	Х	х	х	х	х	Q12W	х	х
Emicizumab ADA (plasma) b, d		Х				х		х			х		х		х		х	Q12W	х	Х
PD and safety biomarkers (plasma) ^{b, e, f}		Х	х	х	х	х	х	х	х	х	х	х	х	х	х	x	х	Q12W	х	х
Anti-FVIII antibodies f	x ^g	Х						х			Х			Х			х	Q12W	Х	Х
Plasma and serum sample for bone and joint biomarkers h, f		X									х						х			х
Plasma samples following treatment with coagulation factor product i									ا	Moni	torin	g for	proc	oagu	lant	effec	t ⁱ			

ADA=anti-drug antibody; Discon.=discontinuation; FU=follow-up; FXIa=factor XIa; FVIII=factor VIII; PD=pharmacodynamic; PK=pharmacokinetic; Q12W=every 12 weeks; TGA=thrombin generation assay.

Note: All study visits and assessments during the treatment period should be performed within ± 2 days of the scheduled date until safety follow-up visit. Safety follow-up visit should be performed 24 weeks after discontinuation of emicizumab; deviation of ± 7 days is acceptable. Safety follow-up visit will not be performed for patients who transfer to commercial emicizumab. On treatment days, all assessments should be performed prior to emicizumab dosing, unless otherwise specified. On treatment days, all PRO assessments, when applicable, should be performed prior to any study intervention,

Emicizumab—F. Hoffmann-La Roche Ltd 98/Protocol BO41423, Version 3

Appendix 2:Schedule of Pharmacokinetic, Immunogenicity, and Biomarker Samples (cont.)

- ^a Study completion/discontinuation visit occurs when the patient completes 52 weeks of emicizumab treatment in the study and either transfers to commercially available emicizumab or receives further emicizumab per Roche Global Policy on Continued Access to Investigational Medicinal Products; OR patient has completed the 24-week safety follow-up visit after emicizumab discontinuation; OR patient has withdrawn consent; OR patient is lost to follow-up.
- ^b Samples should always be drawn pre-dose.
- ^c If the sample is missed on Day 1, it can be collected at any other scheduled visit.
- ^d ADA samples may also be drawn if hypersensitivity event occurred or at any time (unscheduled) in the investigator's judgment.
- e PD markers include FVIII activity (bovine and human coagulation factor chromogenic assays), FVIII protein, and thrombin generation (FXIa- and tissue factor triggered TGAs). Safety markers include, but are not limited to, fibrinogen, D-dimer, and prothrombin fragment 1+2.
- f Samples will only be collected if the permitted blood volumes allow (based on patient body weight as described in Section 4.5.5). Refer to the laboratory manual for details.
- ^g At screening, the evaluation for anti-FVIII antibodies will be performed locally and documented on eCRF to confirm the negative testing for inhibitor as per inclusion criteria. This sample must be obtained during screening, within 4 weeks prior to enrollment (i.e., before initiation of Week 1, Day 1 assessments). The results must be available before enrollment, and local testing will not replace the central laboratory inhibitor testing performed at Week 1.
- h Collect after fasting overnight in patients ≥ 12 years of age.
- Following treatment with coagulation factor product, sample should be collected *for* central laboratory monitoring of emicizumab pharmacokinetics, fibrinogen, FVIII activity (bovine and human coagulation factor chromogenic assays), D-dimer, prothrombin fragment 1 + 2, and thrombin generation (FXIa- and tissue factor-triggered TGAs) within 24 hours (but no later than 48 hours) of initial coagulation factor product use. If a breakthrough bleed occurs outside of a hospital visit and requires treatment, collection of a blood sample should occur within 30 minutes–24 hours but no later than 48 hours after treatment for the bleed has been administered. In such a case, to avoid requiring patients to return to the study site for a blood draw, this sample collection may be performed by a mobile nursing professional at the patient's home or another suitable location to improve access and convenience for patients participating in the study.

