4. MATERIALS AND METHODS

4.1 PATIENTS

Approximately 70 patients of all age groups will be enrolled in the study consisting of approximately 20 patients with mild and approximately 50 patients with moderate hemophilia A without FVIII inhibitors whose phenotype warrants prophylaxis.

4.1.1 Inclusion Criteria

Patients must meet the following criteria for study entry:

- Signed Informed Consent Form (signed by patient's legally authorized representative for patients who have not attained the age of majority)
- Signed Assent Form when appropriate, as determined by patient's age and individual site and country standards
- Willingness and ability to comply with schedules visits, treatment plans, laboratory tests and other study procedures
- Diagnosis of mild (FVIII level between > 5% and < 40%) or moderate (FVIII level between ≥ 1% and ≤ 5%) congenital Hemophilia A without FVIII inhibitors
- Weight ≥3 kg
- Need for prophylaxis based on investigator assessment
- A negative test for inhibitor (i.e., <0.6 BU/mL) within 8 weeks prior to enrollment
- No documented inhibitor (i.e., < 0.6 BU/mL), FVIII half-life < 6 hours, or FVIII recovery < 66% in the last 5 years

Patients who completed successful immune tolerance induction (ITI) at least 5 years before screening are eligible, provided they have had no evidence of inhibitor recurrence (permanent or temporary) as may be indicated by a detection of an inhibitor, FVIII half-life <6 hours or FVIII recovery <66% since completing ITI (Antun et al. 2015).

Emicizumab—F. Hoffmann-La Roche Ltd 35/Protocol BO41423, Version 3

- Documentation of the details of prophylactic or episodic FVIII treatment and of number of bleeding episodes for at least the last 24 weeks prior to enrollment
- Adequate hematologic function, defined as platelet count ≥100,000 cells/µL and hemoglobin ≥8 g/dL (4.97 mmol/L) at the time of screening
- Adequate hepatic function defined as total bilirubin ≤1.5×age-adapted upper limit of normal (ULN) (excluding Gilbert syndrome) and both AST and ALT ≤3×age-adapted ULN at the time of screening, and no clinical signs or known laboratory/radiographic evidence consistent with cirrhosis
- Adequate renal function, defined as serum creatinine ≤2.5 × age-adapted ULN and creatinine clearance ≥30 mL/min by Cockroft-Gault formula
- For women of childbearing potential: agreement to remain abstinent (refrain from heterosexual intercourse) or use contraception as defined below:

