4.1.2 Exclusion Criteria

Patients who meet any of the following criteria will be excluded from study entry:

- Inherited or acquired bleeding disorder other than mild (FVIII level between > 5% and <40%) or moderate (FVIII level between ≥1% and ≤5%) congenital hemophilia A
- History of illicit drug or alcohol abuse within 48 weeks prior to screening, in the investigator's judgment

Emicizumab—F. Hoffmann-La Roche Ltd 36/Protocol BO41423, Version 3

- Previous (within the last 12 months) or current treatment for thromboembolic disease (with the exception of previous catheter-associated thrombosis for which anti-thrombotic treatment is not currently ongoing) or signs of thromboembolic disease
- Other conditions (e.g., certain autoimmune diseases) that may currently increase the risk of bleeding or thrombosis
- History of clinically significant hypersensitivity associated with monoclonal antibody therapies or components of the emicizumab injection
- Planned surgery during the emicizumab loading dose phase
 Surgeries in patients on emicizumab from Week 5 onwards are allowed.
- Known HIV infection with CD4 counts < 200 cells/μL
- Concomitant disease, condition, significant abnormality on screening evaluation or laboratory tests, or treatment that could interfere with the conduct of the study, or that would in the opinion of the investigator, pose an additional unacceptable risk in administering study drug to the patient
- Receipt of any of the following:
 - An investigational drug to treat or reduce the risk of hemophilic bleeds within 5 half-lives of last drug administration with the exception of prior emicizumab prophylaxis (prior investigational or commercial emicizumab use is not an exclusion criterion)
 - A non-hemophilia-related investigational drug within last 30 days or 5 half-lives, whichever is shorter
 - Any other investigational drug currently being administered or planned to be administered
- Inability to comply with the study protocol in the opinion of the investigator
- Pregnant or breastfeeding, or intending to become pregnant during the study
 Women of childbearing potential must have a negative serum pregnancy test result within 7 days prior to initiation of study drug.

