4.5.1 Informed Consent Forms and Screening Log

Written informed consent/assent for participation in the study must be obtained before performing any study-related procedures (including screening evaluations). Informed Consent/Assent Forms for enrolled patients and for patients who are not subsequently enrolled will be maintained at the study site.

All screening evaluations must be completed and reviewed to confirm that patients meet all eligibility criteria before enrollment. The investigator will maintain a screening log to record details of all patients screened and to confirm eligibility or record reasons for screening failure, as applicable.

Emicizumab—F. Hoffmann-La Roche Ltd 43/Protocol BO41423, Version 3

4.5.2 Medical History, Concomitant Medication, and Demographic Data

Medical history, including clinically significant diseases, procedures, use of alcohol and drugs of abuse within the past year, and medical allergies will be recorded at baseline. In particular, sites should record whether the patient has any history of prior ITI, anaphylaxis, or known thrombophilia. For female patients, fertility status, and menstruation and menorrhagia history data will be recorded at baseline. In addition, all medications (including prescription, over-the-counter, and herbal/homeopathic remedies and therapies) used by the patient within 4 weeks prior to enrollment will be recorded. All bleed information (i.e., start date, cause, type, location) during the 24 weeks prior to study entry should be documented.

Demographic data will include age, sex, and self-reported race/ethnicity. Race and ethnicity are standard data points in clinical trials conducted by Roche, collected as part of the demographics, as there is potential that diseases might affect racial groups differently.

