5.1.1.4 Thrombotic Microangiopathy

TMA is used to describe a group of disorders with clinical features of microangiopathic hemolytic anemia, thrombocytopenia, and organ damage that can include the kidneys, gastrointestinal system, central nervous system, etc.

Three cases of TMA were reported in Study BH29884. All cases were assessed as being related to study treatment and occurred after recent concomitant aPCC use. This

Emicizumab—F. Hoffmann-La Roche Ltd 59/Protocol BO41423, Version 3

study will be conducted in patients without FVIII inhibitors, and aPCC is therefore not expected to be used for the treatment of breakthrough bleeds. For further details on TMAs, refer to the RO5543262 (Emicizumab) Investigator's Brochure.

Any TMA event should be reported as an adverse event of special interest and also as a serious adverse event, if it meets criteria for such (see Sections 5.2.2 and 5.2.3).

5.1.1.5 Life-Threatening Bleeding Due to Unreliable Standard Coagulation Tests and Inhibitor Assays in the Setting of Emicizumab

Coagulation laboratory tests (including, but not limited to, aPTT, one-stage FVIII activity, and FVIII inhibitor measurement by Bethesda assay) are not reliable and do not accurately reflect the patient's underlying hemostatic status while receiving emicizumab prophylaxis (see Table 1). In one-stage assays, emicizumab is associated with a supraphysiologically short-time-to-clot formation and, thus, normalization of aPTT at subtherapeutic levels and an overestimation of true FVIII activity. Emicizumab is not recognized or neutralized by FVIII inhibitors, and therefore cannot be detected by a functional test such as Bethesda or Nijmegen-Bethesda assays, which use a one-stage clotting-based readout. Furthermore, emicizumab activity cannot be detected by chromogenic assays using purified bovine coagulation proteins and can only be detected using an assay composed of human proteins. See the RO5543262 (Emicizumab) Investigator's Brochure for additional details as to which tests can be used and how the test results can be interpreted.

Because of the long half-life of emicizumab, these effects on coagulation assays may persist for up to 6 months after the last dose.

There is a risk of life-threatening bleeding due to unreliable standard coagulation tests and inhibitor assays in the setting of emicizumab in the market setting by practitioners, particularly for emergency care practitioners.

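### For patients given emicizumab in the 6 months before screening, the only inhibitor result required before enrollment is a local test of unspecified assay type

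*Protocol*

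**What the plan says.** The inclusion criterion in Protocol Section 4.1.1 is: "A negative test for inhibitor (i.e., <0.6 BU/mL) within 8 weeks prior to enrollment". It does not name an assay. Appendix 2, footnote g, assigns the test to the site: "At screening, the evaluation for anti-FVIII antibodies will be performed locally and documented on eCRF to confirm the negative testing for inhibitor". It continues: "The results must be available before enrollment, and local testing will not replace the central laboratory inhibitor testing performed at Week 1". So the local result gates entry, and the central test is a Week 1 sample. Footnote f, attached to the same row, adds a condition: "Samples will only be collected if the permitted blood volumes allow".

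Section 4.1.2 excludes recent investigational drugs for bleed prevention but exempts emicizumab: "prior investigational or commercial emicizumab use is not an exclusion criterion". It sets no washout.

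Section 5.1.1.5, in a list of tests affected by emicizumab, says: "FVIII inhibitor measurement by Bethesda assay) are not reliable". It explains that Bethesda and Nijmegen-Bethesda assays have a one-stage clotting read-out, that one-stage assays overestimate FVIII activity on emicizumab, and that the effects may last up to 6 months after the last dose. It also says that bovine-reagent chromogenic assays do not detect emicizumab.

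On treatment history, Section 4.5.2 covers all medications "used by the patient within 4 weeks prior to enrollment will be recorded". The 24-week record in Section 4.1.1 is: "Documentation of the details of prophylactic or episodic FVIII treatment and of number of bleeding episodes".

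**The concern.** Section 5.1.1.5 warns about a class of test, and the eligibility rule does not carry that warning over to the patients it concerns. A BU/mL limit points to a Bethesda-type titre, and nothing in Section 4.1.1 or footnote g stops a site from using a clotting-based one in a patient who still has emicizumab in plasma.

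If an inhibitor were missed, the patient would be enrolled and could be dosed before any central result was known. Breakthrough bleeds are to be treated with FVIII, whereas Section 3.3.4 says an inhibitor would change bleed management and call for bypassing agents. Section 5.1.1.4 expects no aPCC use because patients lack inhibitors, and that reasoning would not hold for such a patient.

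**Working it through.** There is no sample-size or power figure to reproduce. The check sets the rules side by side and compares time windows.

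1. **Can a recent user enter?** Yes. Section 4.1.2 exempts prior emicizumab from the 5-half-life washout. Section 4.4.2 bars drugs affecting hemostasis for at least 4 weeks before treatment. Even if that were read to cover emicizumab, 4 × 7 = 28 days is well short of 6 months (365.25/2 ≈ 183 days). Such patients are plausible, since Section 5.1 says several countries already approve emicizumab for mild and moderate disease.

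2. **Can the entry test fall within the interference period?** Yes. The test may be up to 8 × 7 = 56 days before enrollment under Section 4.1.1, or 4 × 7 = 28 days under footnote g. A patient dosed within about 183 days before the sample is still in the period named in Section 5.1.1.5, wherever the sample falls in either window.

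3. **Which way would the error go?** Section 5.1.1.5 says one-stage assays overestimate FVIII activity on emicizumab, and that FVIII inhibitors do not neutralize emicizumab. An inhibitor titre read from residual clotting activity would then tend to look too low, which means a missed inhibitor. This is an inference; the protocol says only that the test is unreliable.

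4. **Does any other result required before enrollment correct this?** No.
   - The central inhibitor test is sampled at Week 1, and its result is not an entry condition.
   - The bovine chromogenic assay in Section 3.3.5 is named for FVIII activity, and Appendix 2 samples it from Day 1.
   - The 5-year criterion in Section 4.1.1 (no documented inhibitor, short half-life or low recovery) helps only where one of these was already on record.

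5. **Would the site know beforehand that the patient is a recent user?** Not necessarily from the required records. The medication history covers 28 days. The 24-week record concerns FVIII treatment and bleeds, and a patient on emicizumab can still have had episodic FVIII.

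6. **What shows up after enrollment?**
   - Appendix 2 schedules a pre-dose emicizumab PK sample on Day 1, and SAP Section 3.4 confirms it. That row does not carry footnote f, so residual emicizumab should be measurable. In small children, however, Section 4.5.5 ranks PK after safety laboratory tests.
   - Central inhibitor tests fall at Weeks 1, 13, 25, 37 and 49, then every 12 weeks. They can show an inhibitor if the central assay is suitable; the documents do not name it.

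7. **Size.** The number of recent users is not stated. Each is 1/70 = 1.43% of the planned sample. That is the weight of one prior user; no rate is given for misclassification among them.

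**The case against.** The case against has real weight.

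- **Several conditions must coincide.** The patient must have had emicizumab within 6 months, have an inhibitor now with nothing documented in 5 years, and be tested with a clotting-based assay at a site that overlooks Section 5.1.1.5. The plan mainly expects patients coming from FVIII: EmiPref contrasts emicizumab with earlier IV treatment, and SAP Section 3.3.3 classes the prior regimen only as episodic or prophylactic. The EU label is limited to severe disease.
- **Assay choice may be settled elsewhere.** Section 5.1.1.5 refers to the Investigator's Brochure, and footnote f to the laboratory manual. Neither was available for this review.
- **Harm is limited.** Section 1.2.1 says emicizumab works whether or not inhibitors are present. Section 4.4.1 permits bypassing agents, with limits on aPCC. Central testing is repeated, and footnote f is in effect a pediatric weight limit.

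Most of this stands, and it lowers the importance of the point. What it does not do is put a suitable result in hand before enrollment: the protocol text makes no particular assay a condition of entry, and the safeguards within the study act later.

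A reader might go further and infer that sites or the central laboratory use the wrong assay, that screening is unsound for the whole trial, or that affected patients could never be identified. The documents support none of these. They do not say which assay is used, emicizumab-naive patients are unaffected, and the Day 1 PK sample can identify recent users in the data.

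**Conclusion.** The point holds as a narrow gap in eligibility and safety, of minor importance. For patients given emicizumab within 6 months before screening, the protocol accepts as its only pre-enrollment inhibitor check a local result below 0.6 BU/mL from any assay, including a type it elsewhere calls unreliable.

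The conclusion assumes that at least one recent user enrolls and that no document outside those reviewed already imposes a suitable assay. If there are no recent users, there is no effect.

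A reader might also infer that the primary ABR analysis is at risk, because a misclassified patient would stay in the Treated population (SAP Section 3.1.2). That does not follow. The number may be zero, one patient is 1.4% of the planned 70, and emicizumab is expected to act regardless of inhibitors.

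**What to change.** In Section 4.1.1 and Appendix 2, footnote g, add one sentence to this effect: *for any patient given emicizumab within 6 months before screening, the negative inhibitor result must come from an assay with an emicizumab-insensitive read-out (for example bovine-reagent chromogenic), run locally or centrally, and must be available before enrollment.* On the eCRF, record any emicizumab use in those 6 months with the date of the last dose, and record which inhibitor assay was used.

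The cost is one sentence in each of two places and two eCRF items, with no extra visits. The downside is that a few screening samples may need central testing. The result must then return within the 4-week limit between screening and enrollment in Section 4.2, or the patient is rescreened. No SAP change is needed. The amendment is optional but cheap.
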